### **10.3. Study limitations**

The clinician performing the procedure cannot be blinded to the assignment of the treatment arm. The intervention is limited to the intraoperative period since the patients are extubated in the operating room. The follow up of postoperative morbidity and mortality is limited to one month. The study is not designed to have sufficient power to detect significant differences in major postoperative complications.

#### **10.4. Efficacy analysis:**

Efficacy analysis will be performed in two different populations: Intention-to-treat (ITT) analysis and per-protocol analysis. In an ITT population, none of the patients are excluded and the patients will be analyzed according to the randomization scheme. In a per-protocol analysis, only patients who complete the entire clinical trial according to the protocol will be counted towards the final results.

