## 5. CLINICAL TRIAL DESIGN

### 5.1. Outcome measures

#### Primary outcome measures:

- Percentage of the intraoperative time in which the cardiac index is equal or superior to 2.2 l/min/m^2 (%) [Time Frame: During the total duration of the surgery].

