#### Secondary outcome measures:

- Oxygenation and tissue perfusion markers [ Time Frame: Within 24 hours after lung surgery]

- Fluid balance [ Time Frame: After 24 hours of finalization of lung surgery]

1) Inputs:
+ Fluid therapy (intra and postoperative, ml):
+ Insensible fluid input (due to oxidation): 300 ml/24 hours (12.5 ml/h).
+ Oral intake (water, ml):
2) Outputs:
+ Intraoperative bleeding (ml)
+ Urine output 24 hours (ml)
+ Insensible fluid loss: 0.5 ml/kg/h (24h)
+ Intrathoracic drainage (ml)
+ Thoracotomy: 1ml/kg/h surgery (0.5 ml/kg/h in case of video-assisted thoracotomy)

- Observation of acute kidney injury (AKI) [ Time Frame: After 72 hours of finalization of lung surgery]

The AKIN classification/staging system of acute kidney injury		
Stage	Serum creatinine	Urine Output (UO)
1	↑ SCr ≥26.5 μmol/L (≥0.3 mg/dL) or ↑SCr ≥150 a 200% (1.5 a 2×)	UO < 0.5 ml/kg/h during > 6 h
2	↑ SCr >200 a 300% (>2 a 3×)	UO < 0.5 ml/kg/h during > 12 h
3	↑ SCr >300% (>3×) or if baseline SCr ≥353.6 μmol/L (≥4 mg/dL) ↑SCr ≥44.2 μmol/L (≥0.5 mg/dL)	UO < 0.3 ml/kg/h during > 24 h or anuria during 12 h
Stage 3 also includes patients requiring RRT independent of the stage (defined by SCr and/or UO) they are in at the moment they initiate RRT.		

- Observation of acute respiratory distress syndrome (ARDS) [ Time Frame: Within 30 days after lung surgery]

The Berlin Definition of Acute Respiratory Distress Syndrome.
a) Timing: Within 1 week of a known clinical insult or new or worsening respiratory symptoms.
b) Chest imaging: Bilateral opacities, not fully explained by effusions, lobar/lung collapse, or nodules.
c) Origin of edema: Respiratory failure not fully explained by cardiac failure or fluid overload. Need

objective assessment (eg. Echocardiography) to exclude hydrostatic edema if no risk factor present.	
d) Oxigenation:	
Mild	200 mm Hg < PaO 2 /FIO 2 ≤ 300 mm Hg with PEEP or CPAP ≥ 5 cm H 2 O *
Moderate	100 mm Hg < PaO 2 /FIO 2 ≤ 200 mm Hg with PEEP ≥ 5 cm H 2 O
Severa	100 mm Hg ≤ PaO 2 /FIO 2 with PEEP ≥ 5 cm H 2 O
* CPAP may be delivered noninvasively in the mild acute respiratory distress syndrome group.	

- Duration of hospital stay [ Time Frame: Within 30 days after lung surgery]
- Mortality [ Time Frame: Within 30 days after lung surgery ]

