**Arm A: Conventional hemodynamic management**

On the basis of a continuous infusion of 2 ml/kg/h of balanced crystalloid solution (restrictive fluid therapy), the clinician will try to get basic intraoperative hemodynamic objectives: Heart rate 60-100 beats per minute, mean arterial pressure 65 mm Hg, serum lactate 2 mmol / L, oxygen saturation 95% (90% during one lung ventilation). The use of fluids and vasoactive agents will be at the discretion of the operating room anesthesiologist. The total of fluids administered in the intraoperative period will be fixed in a maximum of 2000 ml of crystalloid solutions.

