#### **5.4. Procedures of the study and treatment duration**

Patients undergoing thoracic surgery will have a preanesthesia evaluation. Once the surgical programming of the week is published, the inclusion criteria and the absence of exclusion criteria will be checked. We are going to compare two interventions: the use of goal-directed therapy versus conventional hemodynamic management.

The anesthetic technique will be the same in both groups, as well as the invasive techniques used (epidural, double lumen tube placement, arterial route, central line). The intervention finishes when the patient is extubated in the operating room, so both groups of patients will receive the same treatment in the postoperative period.

The patient will undergo daily clinical follow-up during the admission to monitor the appearance of complications, as well as to check the survival at first month. The detailed schedule of procedures is included in section 7.

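### The per-protocol set in 10.4 requires completion of the whole 30-day trial, so patients with a full intraoperative record can leave the primary-outcome analysis because of later events

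*Combined protocol and SAP*

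**What the plan says.** Section 10.4 plans two analyses: "Efficacy analysis will be performed in two different populations: Intention-to-treat (ITT) analysis and per-protocol analysis". For ITT, "none of the patients are excluded and the patients will be analyzed according to the randomization scheme". For per-protocol, "only patients who complete the entire clinical trial according to the protocol will be counted towards the final results". Neither set is named as primary, no outcome is assigned to one set or the other, and completion is not defined.

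The time points come from other sections:

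- Primary outcome (5.1): "Time Frame: During the total duration of the surgery".
- Treatment (5.4): "The intervention finishes when the patient is extubated in the operating room".
- Follow-up (10.3): "The follow up of postoperative morbidity and mortality is limited to one month". Appendix III places the end of follow-up at day +30, with adverse events and survival as the assessments.
- Mortality (5.1, secondary): "Mortality [ Time Frame: Within 30 days after lung surgery".
- Withdrawal (6.3): the reasons include transfer to the ICU, and instability of cardiac origin or massive haemorrhage that forces closer monitoring.

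Section 8.1 says that efficacy is evaluated in every randomised patient. Sections 9.1 and 10.5 set the safety analysis as ITT.

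**The concern.** A per-protocol analysis should show the effect in patients who received the allocated strategy as planned. Here that strategy is delivered, and the primary outcome fully observed, in the operating room. Membership of the set, however, is settled a month later. Events in between say nothing about whether the haemodynamic strategy was followed, but several of them could be consequences of it.

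At stake is how the per-protocol result can be read. If it differs from ITT, nobody can tell whether the difference reflects adherence or the removal of patients with poor postoperative courses. Because 10.4 does not rank the two sets, the plan also gives no answer as to which result carries the conclusion when they disagree.

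**Working it through.** **1. Timeline.** Randomisation follows arterial line placement (5.2; 5.3, step 13). Then come surgery (primary outcome window), extubation (end of intervention), 72 hours (AKI window) and day 30 (ARDS, hospital stay and mortality windows; last contact). The rule in 10.4 takes the last of these as the condition for all efficacy outcomes.

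**2. The rule applied to patients with a complete intraoperative record.**

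| Later event | ITT | Per-protocol as written | Does the event show non-adherence? |
|---|---|---|---|
| None, day 30 contact made | in | in | no |
| Day 30 contact missed | in | out | no |
| Postoperative ICU transfer (6.3) | in | out | no |
| Cardiac instability or massive haemorrhage (6.3), strategy applied to the end of surgery | in | out | no |
| Death before day 30, recorded | in | undefined | no |

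The three rows marked out lose a patient whose primary outcome was already known. Two of them depend on clinical events that the strategy might affect.

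**3. Mortality, under both readings of completion.** The inputs are 15 patients per arm (10.1) and Fisher's exact test (10.2). The death counts are illustrative.

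- Death counts as non-completion: the table is 0/n v 0/n whatever happens. With 3 v 0 deaths, ITT is 3/15 v 0/15 (p = 0.224) and per-protocol is 0/12 v 0/15 (p = 1.0). With 2 v 0, ITT p = 0.483 and per-protocol is 0/13 v 0/15 (p = 1.0). Chi-squared cannot be computed, because expected counts are zero.
- A recorded death counts as completed follow-up: the deaths stay in, and with no other exclusions the per-protocol table equals ITT.

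The documents give no mortality rate. The chance of at least one death among 30 patients is 1 − (1 − p)^30. For assumed p of 1%, 2%, 5% and 10% this is 26.0%, 45.5%, 78.5% and 95.8%. Whether the choice of reading would ever matter thus depends on a rate that the plan does not state.

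**4. Size of the set.** The plan's own figure reproduces only as 15 + 15 = 30; it states no alpha, power, effect size, SD or dropout. Assumed non-completion of 5%, 10% and 20% leaves 30 × 0.95 = 28.5, 30 × 0.90 = 27 and 30 × 0.80 = 24 patients.

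**5. Possible shift in the primary outcome.** Let one patient have value x and let the other 14 in the arm have mean M.

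- Arm mean with the patient: (14M + x)/15. Without: M.
- Shift on removal: M − (14M + x)/15 = (M − x)/15.

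The outcome lies between 0% and 100%, so |M − x| ≤ 100 and the shift is at most 100/15 = 6.7 percentage points. It is upward if the removed patient was below the others, downward if above, and zero if equal. The documents give neither x nor M, so this is a bound and not an estimate.

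**The case against.** The strongest reply is that nothing is lost. ITT keeps every randomised patient for efficacy, safety is ITT as well, and 8.1 already points to all randomised patients. Both analyses are prespecified, so reporting only the more favourable one would itself depart from the plan. All of this stands. It limits the problem to the per-protocol set and to the missing statement of which set leads; it does not repair the per-protocol rule.

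Four stronger readings are tempting, and the documents do not support them.

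- **Per-protocol mortality must be empty.** This needs death to count as non-completion. Survival is itself a day 30 assessment, so a recorded death can equally be read as completed follow-up. It is also unclear that mortality gets a per-protocol analysis: the efficacy list in 8.1 omits it, and death is a serious adverse event (9.2) covered by the ITT safety analysis. That omission does not settle the matter, since 8.1 also leaves out lactate, fluid balance and hospital stay, all secondary outcomes or objectives.
- **The set differs by arm because of a fluid ceiling.** Arm A fluids "will be fixed in a maximum of 2000 ml of crystalloid solutions", but Arm B's algorithm is in a figure that is not shown, and no section lists deviations that remove a patient.
- **The per-protocol result is the trial's final result.** The closing words of the definition say who counts within a per-protocol analysis; they do not rank it above ITT.
- **The exclusions favour one arm by a known amount.** Neither direction nor size can be derived, as the working shows.

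**Conclusion.** The concern holds for the per-protocol set. As written, 10.4 makes membership depend on events up to 30 days after an intervention and a primary outcome that both end on the day of surgery. Patients with complete primary-outcome data are removed for later loss or for a withdrawal under 6.3, which is selection on post-randomisation events and not on adherence.

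This rests on reading the entire trial as running to the day 30 contact, which Appendix III supports, and on treating a patient withdrawn under 6.3 as not having completed. The effect of the exclusions is unknown; only the bound of 6.7 percentage points in an arm mean for one removed patient follows from the design. The statement on mortality is conditional on an undefined term.

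ITT protects the trial's main comparison, so this is a flaw in a second analysis, plus a missing hierarchy. It is worth correcting because the stated rule would give a result that cannot be interpreted.

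**What to change.** In 10.4:

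1. Name ITT as the primary population, consistent with 8.1, and per-protocol as supportive.
2. Define per-protocol by intraoperative criteria only: eligible, resection performed, allocated strategy applied from randomisation to the end of surgery, and a usable EV1000 record. Judge eligibility on what was known before randomisation. Section 6.2 excludes patients who will go to critical care after surgery, and an unplanned transfer should not re-enter the definition by that route.
3. State that death, postoperative ICU transfer or a missed day 30 contact does not remove a patient from the set.
4. Do not use per-protocol for mortality, ARDS, AKI or hospital stay.

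Reconcile 6.3 with 10.4, so that withdrawal under 6.3 does not by itself take data already collected out of the analysis. This concerns the use of data only and leaves the clinical reasons for withdrawal as they are. An event that stops the allocated strategy during surgery would still exclude a patient under item 2. Some selection therefore remains, which is a further reason to keep per-protocol supportive.

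Cost: rewording of 10.4 and a sentence in 6.3, with no new patients or measurements. The per-protocol results for postoperative outcomes are given up.

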#### **10.5. Safety analysis:**

The safety analysis will be performed by intention to treat (ITT) in all randomized patients.

### **11. ÉTHICAL CONSIDERATIONS**

#### **11.1. Introduction**

GDT-Thorax will be carried out in accordance with the Declaration of Helsinki principles (appendix II) and the legal norm directive 2001/20/EC of the European Parliament and of the Council of 4 April 2001 on the approximation of the laws, regulations and administrative provisions of Member States relating to the implementation of Good Clinical Practice in the conduct of clinical trials on medicinal products for human use. Moreover, all local applicable rules such as Spanish Royal Degree 223/2004 will be considered for development of the study.

The trial will start after obtaining approval from a Central Ethics Review Committee (Clinical Research Andalusian Central Ethics Review Committee, CCEIBA), conformity from the Directors of the Institutions, and the authorization of the local ethic committee. A formal contract agreement was signed between each institution and the sponsor of the study.

#### **11.2. Informed consent**

The subject of the trial will grant his/she consent after having understood, through a previous interview with the investigator, the objectives of the trial, risks and drawbacks, as well as the conditions under which it will be carried out, and after being informed of their right to withdraw from the trial in any time without causing any harm.

Each study candidate patient will be provided with the corresponding informed consent in which the purposes of the research will be explained in addition to the procedures to be used, the expected duration of the research and the expected benefits to the patient and others.

Finally, each patient will be informed of the intention of publishing the results of the study in a scientific publication. To include a patient in the trial, he/she must give his or her informed consent to all assumptions.

Consent will be documented through an information sheet for the subject and the consent form. When the subject of the trial is unable to giving consent:

- If the subject is an adult without the capacity to give informed consent, the investigator will obtain the consent of the legal representative, having been informed about the possible risks, discomforts and benefits of the trial. The consent shall reflect the alleged wish of the subject and may be withdrawn at any time without detriment to him. When the conditions of the subject allows it, he/she shall also give its consent to participate in the trial, after having received all the relevant information adapted to their level of understanding. In this case, the investigator shall take into account the wish of the person unable to withdraw from the trial.
- When the subject is not able to make decisions due to physical or psychic state and has no legal representative, consent will be provided by individuals linked to him for family or de facto reasons. The subject participating in a clinical trial, or their legal representative, may revoke their consent at any time, without further explanation and without detriment to him.

### **11.3. Quality of data**

There will be an exhaustive control of the data quality. CRF will be reviewed by the person in charge of monitoring. Investigators will fulfill the CRF, not knowing the the assigned treatment. Patients data will be exported to a SPSS database.

### **11.4. Protection of data**

The confidentiality of records which could identify subjects in the GDT-Thorax study will be protected in accordance with the EU Directive 2001/20/EC. All laws on the control and protection of personal information will be carefully followed. The identity of patients will not be disclosed in the CRF; names will be replaced by an alphanumeric code and any material related to the trial such as samples will be

identified in the same way so that any personal information can be revealed.

### **11.5. Monitoring and audit**

The study will be monitored through local visits, telephone calls and periodic inspection of CRF with sufficient frequency to check the following:

- Rate of inclusion of patients, compliance with the rules of the protocol procedures, data integrity and accuracy, verification with original documents and occurrence of EA.
- Monitoring visits will be performed by the study monitor. It is understood that she/he may access the medical records of the patients after requesting the researcher, who will facilitate access to the documentation to authorized persons.

### **11.6. Non-compliance**

Non-compliance with the protocol and/or regulatory requirements from an investigator or from the staff members of the promotor should lead to rapid intervention by the promotor, to ensure compliance. If the monitoring and / or audit identify a serious and / or persistent non-compliance on the part of an investigator, the promoter must remove the investigator of the study. When the investigator is withdrawn due to noncompliance, it must promptly notify to the regulatory authorities.

### **11.7. Premature discontinuation**

If the trial ends prematurely or is suspended, the sponsor must inform authorities of the completion or suspension and of the reason for it as specified by the regulatory requirements.

## **12. Financing and insurance policy**

Every economic aspect in this trial will be written in a contract between the promotor and "Fundación Pública Andaluza para la Gestión de la Investigación en Salud de Sevilla".

### **12.1. Insurance policy**

Interventional level in this trial is low, because both interventions are similar to usual clinical practice. We will proceed to request the exemption of the contracting of the insurance policy for the

coverage of the possible civil responsibility that derives from some adverse events demonstrated on the subjects of this study.

### **13. Amendments to the protocol.**

To ensure the study conditions and the valid statistical analysis of the data, neither the researcher nor the sponsor could alter the conditions agreed and stipulated in this protocol. Any amendment to the protocol which may have an impact on the development of the study or potential benefit for the patient, or which may affect patient safety would require a formal amendment to the protocol, such as changes in study objectives, study design, patient population, sample size, study procedures or significant administrative aspects. The study coordinator team and the CTU will agree such an amendment. Then, the amendment will become an integral part of the study protocol. In case the amendments require the approval of the ethical committees and/or Authorities, it must be obtained.

### **14. WORK SCHEDULE**

#### **14.1. PHASES:**

Randomized, controlled, blinded clinical trial with collection, observation and analysis of data.

#### **14.2. RESOURCES AVAILABLE FOR THE REALIZATION OF THE CLINICAL TRIAL:**

The selection, intervention and follow-up of patients will be carried out in: Conventional hospitalization of thoracic surgery, surgery room No. 54 and Post-anesthetic Recovery Unit of the General Hospital Virgen del Rocío. We will have the usual team of surgeons and nurses. There will be an anesthesiologist who will anesthetize all cases to avoid interindividual variability.

For the supervision of the investigation methodology and statistical analysis, we will have the advice of [name] [name], from to the Research Support Unit of the Virgen del Rocío University Hospital (HUVR), together with Dra. [name], from the Clinical Trial Unit of the HUVR.

The staff of the Clinical Trial Unit of the HUVR, will make the request of the clinical trial to the Clinical

Research Andalusian Central Ethics Review Committee, to the CEI of the University Hospitals Virgen Macarena and Virgen del Rocío and will be in charge of the coordination of the project. The assigned personnel will be responsible for the maintenance of the file and the documentation of the trial. A monitoring plan will be made and it will be ensured that the collected data correspond to the source documents and that the procedures indicated in the approved protocol are followed. The staff of the clinical research and clinical trials unit of the HUVR will be responsible for expeditious notification of serious or unexpected adverse events.

4. INVESTIGATION MEDICINAL PRODUCT/DEVICE (Indicate the treatment(s) assigned to the subject after randomization)							
If more space is needed, use copies of this page and tick this box 							
Medicinal product	Dosage and units	Frequency	Route	Start date (dd-mmm-yyyy)	End date (dd-mmm-yyyy) (If this continues, tick this box)	Causal relationship	
						 Related  Not related	
						 Related  Not related	
						 Related  Not related	
Action taken with the medicinal product in response to the AE			 Withdrawal of the medicinal product  Temporary interruption of the medicinal product  Unknown		 Dose reduction  Dose escalation  Without changes  Does not apply		
Did the AE abate after the medicinal product was withdrawn or the dose was reduced?			 Yes  No  Not known  Not applicable				
Did the AE reappear when the medicinal product was reintroduced?			 Yes  No  Not known  Not applicable				
5. CONCURRENT MEDICINAL PRODUCT (Include those concomitant and background treatments that were taken in the two weeks prior to the date of the AE. Do not include the treatment administered to treat AE or that given after the start date of the AE)							
If more space is needed, use copies of this page and tick this box 							
Medicinal product	Daily dose (units)	Frequency	Route	Start date (dd-mmm-yyyy)	End date (dd-mmm-yyyy) (If this continues, tick this box)	Causal relationship	Indication
						 Related  Not related	
						 Related  Not related	
						 Related  Not related	
Action taken with the medicinal product in response to the AE			 Withdrawal of the medicinal product  Temporary interruption of the medicinal product  Unknown		 Dose reduction  Dose escalation  Without changes  Does not apply		
Did the AE abate after the medicinal product was withdrawn or the dose was reduced?			 Yes  No  Not known  Not applicable				
Did the AE reappear when the medicinal product was reintroduced?			 Yes  No  Not known  Not applicable				
